### **10.3.2 Subject Enrollment and Disposition**

The total number of subjects who completed or discontinued the study, and reasons for early discontinuation will be summarized for all randomized subjects.

### **10.3.3 Demographics and Baseline Characteristics**

Demographics and baseline characteristics will be summarized for subjects in different analysis populations and subgroups. Baseline data related to safety and efficacy assessments will be summarized with the post-baseline data in the corresponding safety and efficacy sections.

### **10.3.4 Efficacy Analyses**

The primary efficacy analyses will be performed in subjects in the FAS population except for analyses of PFS, which will be based on the Safety Population. Rules of missing data imputation will be described in the SAP. Analyses based on observed data will be used for sensitivity analyses.

#### **10.3.4.1 Primary Efficacy Analysis**

The primary analysis will be to compare the treatment arms in change from baseline to Week 48 in FVC % predicted based on the FAS Population. A rank ANCOVA model will be used, with baseline FVC % predicted value as covariate, treatment group, stratification, and treatment by stratification interaction as fixed effects. Factors may be eliminated from the model if they are insignificant. If the interaction term is significant, the primary analysis will be based on the subgroup of subjects on first-line therapy.

The ranks of the primary endpoint will be based on observed data and on imputed data if observed data are not available. A detailed description of the rank assessment will be described in the statistical analysis plan. A repeated measures model utilizing all observed data will be used for sensitivity analysis.

Descriptive summaries of the primary efficacy parameter will include the following:

1. Median change from baseline by treatment and visit
2. % of subjects with no decline by treatment and visit
3. % of subjects with decline  $\geq 10\%$  by treatment and visit

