#### **4.3 Treatment Assignment**

Subjects are stratified by prior therapy with pirfenidone and/or nintedanib (yes/no) and randomized 1:1 to FG-3019 or placebo using an Interactive Web Response System (IWRS).

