### 5.1 Inclusion Criteria

1. Age 40 to 80 years, inclusive.
2. Diagnosis of IPF as defined by current international guidelines (Raghu, 2011). Each subject must have one of the following: (1) *Usual Interstitial Pneumonia (UIP) Pattern* on an available HRCT scan; or (2) *Possible UIP Pattern* on an available HRCT scan and surgical lung biopsy within 4 years of Screening showing *UIP Pattern* (HRCT criteria for *UIP Pattern* and *Possible UIP Pattern* and histopathological criteria for *UIP Pattern* described in Appendix 4).
3. History of IPF of  $\leq 5$  years duration with onset defined as the date of the first diagnosis of IPF by HRCT or surgical lung biopsy.
4. Interstitial pulmonary fibrosis defined by HRCT scan at Screening, with evidence of  $\geq 10\%$  to  $< 50\%$  parenchymal fibrosis (reticulation) and  $< 25\%$  honeycombing, within the whole lung, as determined by the HRCT central reader.
5. FVC percent of predicted value  $\geq 55\%$  at Screening.
6. Female subjects of childbearing potential (including those  $< 1$  year postmenopausal) and male subjects with female partners of childbearing potential, must use double barrier contraception methods during the conduct of the study, and for 3 months after the last dose of study drug.

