## 10 STATISTICS

### 10.1 Sample Size Determination

This study is planned to enroll approximately 136 subjects, which will include a target of 110 subjects who are seeking first-line therapy and 26 subjects who failed pirfenidone and/or nintedanib treatment. First-line therapy is defined as no prior therapy with pirfenidone/nintedanib or <10% relative decrease in FVC % predicted while receiving either pirfenidone or nintedanib. Failure of pirfenidone and or nintedanib treatment is defined as having  $\geq 10\%$  relative decrease in FVC % predicted during prior pirfenidone/nintedanib treatment. The effect of first-line treatment is the primary interest of the study, and is the basis for sample size determination. Assuming a 10% dropout rate and a common standard deviation of 7.3, a sample size of 55 subjects per arm in the primary analysis population provides approximately 80% power to detect a treatment difference of 4.2 in change from baseline to Week 48 in percent predicted FVC, using a two-sample t-test at the two-sided significance level of 0.05. The expected treatment difference is estimated using data from study FG-3019-049 and placebo data from published studies. In Study FG-3019-049, a mean decline of 2.8 in % predicted FVC from baseline to Week 48 was observed. The expected decline of 7.0 % predicted FVC in the placebo arm is estimated based on the weighted average of published studies ([Azuma, 2005](#), [Daniels, 2010](#), [Demedts, 2005](#), [King, Jr., 2008](#), [King, Jr., 2009](#), [King, Jr., 2011](#), [Meier-Kriesche, 2004](#), [Noble, 2011](#), [Noth, 2012](#), [Raghu, 2004](#), [Raghu, 2008](#), [Raghu, 2012](#), [Richeldi, 2011](#), [Taniguchi, 2010](#), [Zisman, 2010](#)).

Second line therapy patients are evaluated in an exploratory fashion. If the treatment effect in the pirfenidone/nintedanib failure group is similar to that in the general population, the two subgroups will be combined to achieve higher power.

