#### **10.3.4.2 Analyses of Secondary Efficacy Endpoints**

Similar models to those described above will be applied to analyzing changes in other PFT parameters, HRCT fibrosis score, and patient-reported outcome.

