- a Screening Visit 2 may be combined with Screening Visit 1.
- b Height will be measured only once at Screening Visit 1. Weight will be measured every 12 weeks to determine dose for the subsequent 12-week interval.
- c Including chest auscultation
- d Spirometry (DLCO at first screening test only).
- e Spirometry
- f Pregnancy tests (performed at Screening Visit 1, pre-dose Day 1, and pre-dose at other times) for women of childbearing potential only: serum pregnancy test at Screening Visit 1; urine pregnancy tests at other visits. A positive urine pregnancy test must be confirmed by serum HCG.
- g See Section 11.3.1 for follow-up of AEs.
- h Refer to Section 4.6.1 for prohibited concomitant medications.
- i Vital signs (blood pressure, pulse, respiration rate, and temperature) must be recorded prior to each FG-3019 infusion. Intra-infusion and post-infusion assessments will be performed according to Section 6.3.
- j Subjects who do not complete all visits in the Treatment Period will be encouraged to return for the assessments listed in Appendix 3.

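### The primary rank ANCOVA leaves out screening DLCO and central-read HRCT fibrosis, both already collected before dosing; this causes no bias, but precision may be lost, and the covariate for the secondary models is not named

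*Protocol*

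**What the plan says.** **Primary model.** Protocol 10.3.4.1: "A rank ANCOVA model will be used, with baseline FVC % predicted value as covariate, treatment group, stratification". The sentence continues with a treatment-by-stratification interaction. The section then allows insignificant factors to be removed, and it names a repeated measures model as a sensitivity analysis.

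**Stratification.** Protocol 4.3 stratifies on prior pirfenidone and/or nintedanib (yes/no) and on nothing else.

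**Other severity measures taken before dosing.**
- DLCO: Appendix 1, footnote d, reads "Spirometry (DLCO at first screening test only". Exclusion criterion 12 in section 5.2 uses the value as % predicted.
- HRCT: inclusion criterion 4 in section 5.1 sets limits on fibrosis and honeycombing "within the whole lung, as determined by the HRCT central reader".
- Section 5 says that no eligibility waivers will be granted.

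**Secondary endpoints.** Protocol 10.3.4.2: "Similar models to those described above will be applied to analyzing changes in other PFT parameters, HRCT fibrosis score, and patient-reported outcome". It names no covariate.

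**Sample size.** Protocol 10.1 takes an SD of 7.3 in both arms and a loss of one subject in ten, and states: "a sample size of 55 subjects per arm in the primary analysis population provides approximately 80% power to detect a treatment difference of 4.2". The comparison behind that figure carries no covariates.

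**SAP.** The supplied SAP is Part 2, which covers the extension. Its introduction places the randomized-period analyses in Part 1, which is not among the documents.

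**The concern.** In a trial with 55 subjects per arm in the primary population, any outcome variation that a baseline measurement explains is worth removing from the error term. Here two severity measures besides FVC are recorded before the first dose because eligibility depends on them, and neither is used. Adjustment for prespecified pre-dose values keeps the comparison valid whether or not those values turn out to be prognostic. The balance is therefore favourable: almost nothing is lost if they are uninformative, and precision is gained without new data if they are informative.

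A separate, smaller matter is section 10.3.4.2. The only covariate in the model it refers back to is baseline FVC % predicted. A programmer could take that literally for change in HRCT score or SGRQ and leave out the endpoint's own baseline. A day 1 pre-dose SGRQ and a screening HRCT are both scheduled, so own-baseline adjustment is possible.

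**Working it through.** **1. Inputs from Protocol 10.1.** Difference 4.2, SD 7.3, 55 per arm, 10% dropout, two-sided 0.05, two-sample t-test. Evaluable per arm: 55 × 0.90 = 49.5.

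**2. Reproduce the stated power.** Noncentrality = 4.2 / (7.3 × √(2/49.5)) = 4.2 / 1.467 = 2.86. With 97 df the critical value is 1.985 and the noncentral t gives **80.9%** (normal approximation 81.7%). In reverse, the exact t-test needs 49 per arm for 80%, and 49/0.90 rounds up to 55. The plan's figure stands.

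**3. Power with the two covariates added.** Residual SD = 7.3 × √(1 − R²), where R is the multiple partial correlation of DLCO and HRCT fibrosis with Week 48 FVC change, given baseline FVC and stratum. Degrees of freedom fall by 2, to 95. The equivalent gain in sample size is 1/(1 − R²) − 1.

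| Assumed R | R² | Residual SD | Power | Equivalent extra subjects |
|---|---|---|---|---|
| 0 | 0 | 7.30 | 80.9% | 0% |
| 0.2 | 0.04 | 7.15 | 82.4% | 4% |
| 0.3 | 0.09 | 6.96 | 84.4% | 10% |
| 0.4 | 0.16 | 6.69 | 87.1% | 19% |

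At R = 0 the loss of 2 df costs less than 0.1 percentage point.

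**4. Assumptions in step 3.**
- R is not given anywhere in the documents. The nearest statement, in Protocol 1.6, relates change in HRCT score to change in FVC, without a coefficient. It says nothing about baseline HRCT extent as a predictor.
- 7.3 is treated as the SD left by the planned model, although 10.1 uses it in an unadjusted t-test.
- The calculation is parametric, whereas the planned test works on ranks, partly of imputed values. The percentages show the scale of the gain; they do not predict the power of the rank ANCOVA.

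**5. Secondary models.** If variances at baseline and Week 48 are equal, with correlation ρ, the variance of change is 2σ²(1 − ρ). After adjustment for the endpoint's own baseline it is σ²(1 − ρ²). The ratio is (1 + ρ)/2, which gives 0.85, 0.90 and 0.95 for an assumed ρ of 0.7, 0.8 and 0.9. This saving is at stake only if 10.3.4.2 is read as leaving out the endpoint's own baseline.

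**The case against.** **No loss is demonstrated.** No document shows that baseline DLCO or HRCT extent predicts 48-week FVC change beyond baseline FVC. Eligibility also truncates all three measures (FVC at least 55%, DLCO not below 30%, reticulation from 10% to below 50%), which makes the larger values of R harder to presume. This stands. The table starts at zero gain for that reason, and it would be wrong to say that precision is lost as a matter of fact.

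**The trial is adequately powered as written.** Section 10.1 uses an unadjusted t-test and the figure reproduces. This also stands. The point is an improvement in efficiency and does not correct a sample-size error.

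**Chance imbalance might be read as bias.** A reader might infer that uncorrected imbalance in DLCO or HRCT distorts the treatment comparison. It does not. At R = 0.3 the imbalance contributes 0.3 × 7.3 × √(2/49.5) = 0.44 points (1 SD) to the estimated difference, but that is a part of the standard error of 1.47 already in the test. It is the same R² as in the power table, so it is not a second effect, and the type I error is unaffected.

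**The covariate might be read as fixed for the secondary models.** A reader might infer that 10.3.4.2 adjusts HRCT and SGRQ change for baseline FVC. The text does not say so. A similar model can as naturally mean the endpoint's own baseline, and where the protocol intends baseline FVC to carry over, in the progression-free survival model of 10.3.4.3, it states it. The defect is ambiguity.

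**SAP Part 1 may settle this.** It may name further covariates or own-baseline adjustment, and that cannot be checked here. Sections 10.3.4 and 10.3.4.1 defer imputation and ranking to the SAP but do not expressly defer the choice of covariates. The point therefore holds for the protocol text and is conditional for the final plan.

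**Conclusion.** The concern holds as a low-cost improvement to the protocol's primary model. Two pre-dose severity measures needed for eligibility are left out of it. The omission neither biases the comparison nor invalidates the stated power. The possible gain runs from nothing at R = 0 to about 6 percentage points of power at R = 0.4, and it depends wholly on that assumed correlation and on a parametric approximation to the rank analysis. The case for acting is that the downside is under 0.1 point of power while the possible upside equals 4% to 19% more subjects for R from 0.2 to 0.4. The secondary-endpoint part is a minor clarification of wording. Both parts fall away to the extent that SAP Part 1 already covers them.

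**What to change.** Before unblinding, and unless SAP Part 1 already does so:

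1. In Protocol 10.3.4.1, or in SAP Part 1, prespecify screening DLCO % predicted and baseline HRCT whole-lung fibrosis as fixed covariates, beside baseline FVC % predicted and stratum, in the primary rank ANCOVA and in the repeated measures model. State which HRCT measure is meant: the central reader's extent used for eligibility, or the quantitative score. Section 10.2.3 makes an evaluable baseline score a condition of a separate population, so that score may not exist for everyone.
2. Fill any missing baseline covariate with the overall mean, calculated without regard to arm, so that no subject drops out of the analysis.
3. Exempt these covariates from the provision that insignificant factors may be eliminated. Otherwise the adjustment is not truly prespecified.
4. In 10.3.4.2, state that each HRCT, SGRQ and FVC (litres) model uses the baseline value of the endpoint analysed.

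The cost is a wording change and two degrees of freedom. No new measurements, visits or subjects are needed.

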## **17 APPENDICES**

**Appendix 1. Schedule of Assessments – Randomized Treatment Phase**

Study Period	Screening Period (up to 6 weeks)		Treatment Period																	
	1	2 a	3	4	5	6	7	8	9	10	11	12	13	14	15	16	17	18	19	
Study Days			Day 1 pre dose	Day 1 post dose																
Study Week (± 3 day window for Week 3 to Week 48)	Scr 1	Scr 2 a	0	0	3	6	9	12	15	18	21	24	27	30	33	36	39	42	45	48
Signed and Dated Written Informed Consent	X																			
Inclusion/ Exclusion Criteria	X																			
Demographics	X																			
Medical History	X																			
SGRQ			X					X			X				X					X
Height and Weight b	X b		X					X			X				X					X
Vital Signs	X	X	X	X	X	X	X	X	X	X	X	X	X	X	X	X	X	X	X	X
Complete Physical Exam	X																			X
Focused Physical Exam c			X		X		X		X		X		X		X		X			
Pulmonary Function Tests	X d		X e					X e			X e				X e					X e
CBC with Differential	X		X					X			X				X					X
Serum Chemistry	X		X					X			X				X					X
Spot Urine for Urinalysis	X		X					X			X				X					X
Pregnancy Test f	X		X		X	X	X	X	X	X	X	X	X	X	X	X	X	X	X	X
HRCT of Chest		X									X									X
12-Lead ECG	X										X									X
Serum and Plasma Biomarkers			X								X									X
Plasma HAHA			X																	
Whole Blood for DNA			X																	
AEs and SAEs g	X	X	X	X	X	X	X	X	X	X	X	X	X	X	X	X	X	X	X	X
Concomitant Medications h	X	X	X	X	X	X	X	X	X	X	X	X	X	X	X	X	X	X	X	X
Procedures and Nondrug Therapies	X	X	X		X	X	X	X	X	X	X	X	X	X	X	X	X	X	X	X
Study Drug infusion i			X		X	X	X	X	X	X	X	X	X	X	X	X	X	X	X	

Study Period	Screening Period (up to 6 weeks)		Treatment Period																	
	1	2 a	3	4	5	6	7	8	9	10	11	12	13	14	15	16	17	18	19	
Study Days			Day 1 pre dose	Day 1 post dose																
Study Week (± 3 day window for Week 3 to Week 48)	Scr 1	Scr 2 a	0	0	3	6	9	12	15	18	21	24	27	30	33	36	39	42	45	48
Subject Disposition			X i																	

Abbreviations: AE = adverse event; CBC = complete blood count; DLCO = diffusing capacity of the lungs for carbon monoxide; ECG = electrocardiogram; EX = extended (treatment); HAHA = human anti-human antibody; HCG = human chorionic gonadotropin; HRCT = high resolution computed tomography; SAE = serious adverse event; Scr = screening visit; SGRQ = Saint George’s Respiratory Questionnaire

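### Two pre-treatment spirometries are collected, but the primary model names one baseline FVC covariate; if baseline is a single reading, adding the Screening FVC is a cheap precision gain of uncertain size

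*Protocol*

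**What the plan says.** Protocol 10.3.4.1 compares the arms in change from baseline to Week 48 in FVC % predicted by rank ANCOVA, "with baseline FVC % predicted value as covariate, treatment group, stratification, and treatment by stratification interaction as fixed effects". It also lets model terms be dropped when they are not significant. Section 10.3.4.2 carries the approach over: "Similar models to those described above will be applied to analyzing changes in other PFT parameters".

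In Protocol Appendix 1, the row "Pulmonary Function Tests" is marked at Screening Visit 1 and at Day 1 pre-dose. Footnote d, on the screening mark, reads "Spirometry (DLCO at first screening test only"; footnote e, on the Day 1 mark, is spirometry. Section 4.2.2 has treatment begin within 42 days of the first screening visit.

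The protocol does not say which reading is baseline. SAP Part 2, section 4.3, refers to SAP Part 1 for the randomized-period baseline, and SAP Part 2, section 1, says that Part 1 definitions are not repeated. SAP Part 1 is not among the documents.

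**The concern.** The endpoint is a change score, so error in the baseline reading enters each subject's change in full. Adjusting for that same reading removes little of the error when true FVC varies widely between subjects. A second reading from within the preceding six weeks carries separate information on true FVC at the start of treatment. The trial already collects it, and eligibility depends on it (inclusion criterion 5, with no waivers under section 5), so it should almost never be missing.

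What is at stake is the width of the confidence interval and a few points of power. Both readings precede treatment, so the validity of the comparison is not in question.

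**Working it through.** **1. The plan's own figure.** The inputs in Protocol 10.1 are: "Assuming a 10% dropout rate and a common standard deviation of 7.3, a sample size of 55 subjects per arm". The target stated there is "approximately 80% power to detect a treatment difference of 4.2 in change from baseline to Week 48 in percent predicted FVC". The planned test is a t-test, two-sided at 0.05. Section 4.3 gives the allocation, "randomized 1:1 to FG-3019 or placebo".
- Normal approximation: n = 2 × (1.960 + 0.842)² × 7.3² / 4.2² = 47.4, so 48 per arm. The t-test needs 49 (power 80.5%).
- Dropout: 49 / 0.9 = 54.4, so 55 per arm. The figure reproduces.
- Power at 55 × 0.9 = 49.5 evaluable per arm is 80.9%.

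**2. Model for the covariate question.** The documents give no within-subject or between-subject SD, so these are assumed: measurement error SD s = 2, 3 or 4 points, equal and independent at each visit, and true Day 1 FVC with SD τ = 14. The SD of change from Day 1 is held at 7.3, so the true change has variance Var(D) = 53.29 − 2s². Let λ = τ²/(τ² + s²).

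With Day 1 as the only covariate:

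V₁ = Var(D) + s² + λs²

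The last term is the baseline error left after adjustment. λ is 196/200 = 0.98, 196/205 = 0.956 and 196/212 = 0.925, so 92–98% of the baseline error variance remains.

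Now add Screening. Let a part of the true change, with variance v, be a persistent linear slope that already ran before Day 1, and let k be the screening gap divided by 48 weeks. Then:

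V₂ = V₁ − (λs² − kv)² / (s² + λs² + k²v)

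The two numerator terms oppose each other. A Day 1 value below Screening through error predicts a smaller later decline; one that is lower through real progression predicts a larger one.

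Worked case, s = 3: Var(D) = 35.29, λs² = 8.605, V₁ = 52.89.
- No slope before Day 1: V₂ = 52.89 − 8.605²/17.605 = 48.69, a cut of 8.0%.
- All change from a persistent slope, 6-week gap (k = 0.125, kv = 4.411): V₂ = 52.89 − 4.194²/18.156 = 51.93, a cut of 1.8%.

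**3. Results.** Residual variance with two readings, and the cut against V₁:

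| s | V₁ | No pre-dose decline | Half from slope, 6 weeks | All from slope, 4 weeks | All from slope, 6 weeks |
|---|---|---|---|---|---|
| 2 | 53.21 | 51.27 (3.6%) | 53.07 (0.3%) | 53.21 (0.0%) | 52.86 (0.7%) |
| 3 | 52.89 | 48.69 (8.0%) | 50.60 (4.3%) | 51.10 (3.4%) | 51.93 (1.8%) |
| 4 | 52.08 | 44.98 (13.6%) | 46.23 (11.2%) | 46.60 (10.5%) | 47.35 (9.1%) |

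Power comes from the noncentral t with effect 4.2, 49.5 per arm and the square root of the residual variance as SD, ignoring the stratification terms. One reading gives 80.9%, 81.2% and 81.8%. With no pre-dose decline, two readings give 82.3%, 84.2% and 86.9% (gains of 1.4, 3.1 and 5.2 points). With a fully persistent slope over 6 weeks the gains are about 0.25, 0.7 and 3.5 points; over 4 weeks at s = 2 the gain is nil.

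In subjects, 55 × V₂/V₁ is 53.0, 50.6 and 47.5 per arm in the most favourable column, and 54.6, 54.0 and 50.0 in the last.

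**4. Check on the rank scale.** A rank ANCOVA was simulated with 6,000 trials per setting, 50 per arm, τ = 13 and a small random pre-dose drift of up to 0.9 point. That bound follows from the plan's expected placebo decline: 7.0 × 6/48 = 0.875. The drift was unrelated to later decline. Adding Screening as a second covariate moved power from 79.0% to 79.3% (s = 2), 79.4% to 81.5% (s = 3) and 80.0% to 83.8% (s = 4). The gains have the same order as the t-test approximation and are somewhat smaller.

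**The case against.** A reader might infer that baseline is the Day 1 reading alone, so that its noise is certainly left in the primary comparison. The documents do not support this. The protocol names one covariate, not one reading, and a mean of Screening and Day 1 fits its wording equally well. SAP Part 2 does set the extension baseline for placebo subjects as the last assessment before the first extension dose, but that is an analogy, not the rule for the primary analysis. If SAP Part 1 averages the readings, the gain is already captured. This objection stands, and it makes the point conditional.

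The second objection is that the size rests on assumed SDs, and that calculations with no true decline before Day 1 show close to the best case. This also stands. IPF progresses, and the table shows the gain disappearing at s = 2 and falling to about 2% of variance at s = 3 if decline is a persistent slope. Only at s = 4 does a sizeable gain survive every scenario examined.

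The third is that a single-baseline ANCOVA is a valid, conventional choice. That is true, and it is why this is an optional improvement.

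**Conclusion.** The point holds in conditional form. Two pre-treatment spirometries are scheduled, the model names one baseline FVC term, and the supplied documents leave baseline undefined. If it is a single reading, the Screening value can be added with no new data and no bias. The residual variance falls by about 0–4%, 2–8% or 9–14% for an assumed within-subject SD of 2, 3 or 4 points, or roughly 0–1.5, 1–3 or 3.5–5 power points by the t-test approximation at 49.5 per arm. These ranges rest on a true SD of 14, equal independent errors, and the assumed share of decline that precedes Day 1.

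It would be wrong to conclude that the trial is underpowered or the primary comparison biased. The stated 80% power reproduces without the second reading, and randomisation protects the single-baseline analysis. The importance is low.

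**What to change.** State in 10.3.4.1, or confirm from SAP Part 1, which spirometry or combination defines baseline FVC. If it is the mean of Screening and Day 1, leave the model as it is.

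If it is a single reading, before unblinding:
- keep the endpoint as change from that baseline, and pre-specify Screening FVC % predicted as a second covariate beside the Day 1 value in the rank ANCOVA and the repeated measures sensitivity model;
- do the same in litres for the FVC (L) model;
- exempt the added covariate from the rule on dropping non-significant terms. The two readings will be highly correlated, and keeping one should not depend on the trial's data.

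The cost is one covariate and one degree of freedom, with no new visit or test. The downside is little or no gain if measurement error is small.

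### The test that decides whether the primary analysis narrows to first-line subjects uses prior therapy yes/no, not first-line versus failure, and the fate of a non-significant interaction is left open

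*Protocol*

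**What the plan says.** Protocol Section 10.1 plans 136 subjects: 110 first-line and 26 who failed pirfenidone and/or nintedanib. It states: "The effect of first-line treatment is the primary interest of the study, and is the basis for sample size determination". On the others it says: "Second line therapy patients are evaluated in an exploratory fashion". It also allows pooling: "If the treatment effect in the pirfenidone/nintedanib failure group is similar to that in the general population, the two subgroups will be combined". No criterion for similarity is given. The power statement (55 per arm, about 80%) refers to a primary analysis population that matches the 110 first-line subjects. The Synopsis (Statistical Methods) repeats the sample size and pooling text.

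Section 10.3.4.1 starts elsewhere. The primary analysis is to "compare the treatment arms in change from baseline to Week 48 in FVC % predicted based on the FAS Population", by a rank ANCOVA with baseline FVC % predicted and "treatment group, stratification, and treatment by stratification interaction as fixed effects". Two rules follow: "Factors may be eliminated from the model if they are insignificant", then "If the interaction term is significant, the primary analysis will be based on the subgroup of subjects on first-line therapy". No significance level is attached to either.

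The stratification factor (Sections 4.2 and 4.3) is prior pirfenidone and/or nintedanib, yes or no. The subgroup that the rule switches to is defined differently: "First-line therapy is defined as no prior therapy with pirfenidone/nintedanib or <10% relative decrease in FVC % predicted" while on either drug.

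The SAP supplied is Part 2, for the extension. Its Introduction places the randomized-period analyses in Part 1.

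**The concern.** The switching rule tests one split of the subjects and acts on another. Section 4.2 admits subjects who are intolerant of approved drugs. They are pretreated, so they sit in the yes stratum, yet they count as first-line unless FVC % predicted fell by 10% or more relative. Each such subject dilutes the contrast between strata and makes it less likely that the analysis narrows when failures do not benefit. The full analysis set would then answer a different question, with an average effect of 4.2 x 110/136 = 3.4 rather than 4.2.

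Two further gaps sit in the same paragraph. First, it is optional whether a non-significant interaction is removed. That is exactly the case in which the full set is primary, and the choice decides how the strata are weighted. Second, Section 10.1 defaults to first-line subjects unless effects look similar, while Section 10.3.4.1 defaults to everyone unless they look different. The two part company when the interaction is inconclusive.

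**Working it through.** **Inputs.** From Section 10.1: SD 7.3, difference 4.2, two-sided alpha 0.05, 10% dropout, 110 first-line and 26 failures. Allocation is 1:1 (Section 4.3). Assumed, because the documents give no figure: 0, 8, 14 or 29 pretreated first-line subjects, and an interaction level of 0.05, 0.10 or 0.20. Calculations use normal theory on the unranked scale, without the baseline covariate, with dropouts removed.

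**The plan's own figure.** 55 x 0.9 = 49.5 per arm. The two-sample t-test has 80.9% power there (normal approximation 82%), so the stated 80% is right for first-line subjects. Without dropout, 55 per arm would give 84.9%.

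**A matched switching test.** Evaluable per arm: 49.5 first-line, 11.7 failures.

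- SE of the interaction = 7.3 x sqrt(2/49.5 + 2/11.7) = 3.36.
- For 80% power the effects must differ by 3.36 x (1.960 + 0.842) = 9.4 points.
- For 4.2 versus 0, power is 24% at the 5% level.

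**The written switching test.** With k pretreated first-line subjects the yes stratum has 26 + k subjects and a mean effect of 4.2 x k/(26 + k). The contrast is therefore 4.2 x 26/(26 + k). Its SE is 7.3 x sqrt(2/a + 2/b), with a = 0.45 x (110 - k) and b = 0.45 x (26 + k) evaluable per arm.

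| k | Yes stratum | Contrast | SE | Switches at 5/10/20% level |
|---|---|---|---|---|
| 0 (same as matched) | 26 | 4.20 | 3.36 | 24/35/49% |
| 8 | 34 | 3.21 | 3.05 | 18/28/42% |
| 14 | 40 | 2.73 | 2.90 | 16/25/38% |
| 29 | 55 | 1.99 | 2.69 | 11/19/32% |

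**Power of the whole rule** (simulation, 4 million draws per scenario, non-significant interaction dropped). With no effect in failures:

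- written test, 8 to 29 pretreated first-line subjects: 75-80%
- matched test: 78-82%
- first-line analysis alone: 82%

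The mismatch costs 1.4-1.7 points at k = 8 and 3.1-4.1 points at k = 29. With a uniform effect of 4.2, the rule gives 86-88%.

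If all 136 subjects are kept, as imputation might do, the matched test switches 26% of the time at the 5% level and the written one 12-20%. Power is then 82-85% and 79-84%.

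**Type I error of the rule, term dropped.** Written test with overlap: 5.2-5.7%. Matched test: 5.5-6.0%.

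**Interaction kept or dropped, uniform effect of 4.2.** If it is dropped, strata are weighted by size: SE = 7.3 x sqrt(2/61.2) = 1.320, power 88.9% before switching. If it is kept and the treatment effect is tested with equal stratum weights, the SE is half the interaction SE.

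- Yes stratum 26: 3.356/2 = 1.678, power 70.6% before switching.
- Yes stratum 55: 2.69/2 = 1.34, power about 88%, roughly 1 point below the dropped model.

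After switching, at the three levels, the kept model gives 71/72/74% (stratum 26), 79/79/80% (34), 83/83/83% (40) and 87/87/86% (55).

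**The case against.** The strongest reply is that the governing document is missing. SAP Part 1 may set the level, the model reduction and the weighting. This stands as a limit. However, Sections 10.3.4 and 10.3.4.1 defer to the SAP only the imputation rules and the rank assessment, not the population rule, the factor tested or the model terms.

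Sections 10.1 and 10.3.4.1 also read naturally as one rule: pool unless the interaction shows a difference. That is fair. A reader might infer that the protocol names two contradictory primary populations, but the text does not go that far. What remains is a different default when the interaction is inconclusive. With an interaction SE of 3.36 that is the likely outcome, and it is not evidence of similarity.

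The mismatch is also small in power terms, and zero if no pretreated first-line subject enrols. Both are true. Most of the low switching rate comes from having only 26 failures.

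The elimination sentence stands directly before the switching sentence, so dropping a non-significant term is the ordinary reading. A reader might take the 71-74% as the trial's real power. That needs the term kept, equal stratum weights (which the protocol does not name) and a yes stratum of 26, where the mismatch vanishes. The two problems are not at their worst together. Still, the wording makes elimination optional, and the progression-free survival model in Section 10.3.4.3 includes the same interaction with no elimination clause.

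Two other inferences fail. The sample size is not wrong: its 80% reproduces. Type I error is not seriously inflated by the switch. Choosing the better of the kept and dropped models after seeing results could reach 7.2% at worst (no overlap), but nothing in the documents says the choice would be made that way.

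Finally, all power figures are unranked. The rank ANCOVA cannot be evaluated here because its imputation rule is left to the SAP.

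**Conclusion.** The point holds and should be fixed, though its numerical size is modest. As written, the switching test does not examine the contrast that it decides, unless no pretreated first-line subject enrols. With 4.2 in first-line subjects, 0 in failures and 8 to 29 pretreated first-line subjects assumed, it switches 11-18% of the time at the 5% level instead of 24%, and loses about 1-4 power points across levels of 5-20%. Matching the test does not make it strong.

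Separately, the primary model is not fixed when the interaction is non-significant. Under a uniform effect the two readings give 86-88% (dropped, the more natural reading) and 71-74% (kept, equal weights, yes stratum 26). The gap closes to about 1 point at a stratum of 55.

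The stated 80% is correct, but for first-line subjects only. Confidence is medium, because the overlap is assumed and SAP Part 1 was not available.

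**What to change.** Before unblinding:

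- Define the switching test as treatment by first-line/failure, at a stated level, in a model separate from the primary one.
- Fix the primary rank ANCOVA as treatment, baseline FVC % predicted and randomisation stratum, without the interaction, and delete "Factors may be eliminated from the model if they are insignificant".
- Reconcile the Synopsis and Sections 10.1 and 10.3.4.1 to one default population, including what happens when the interaction is inconclusive.
- State that the 80% power refers to the first-line analysis.

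The cost is wording. No subjects are added, and first-line/failure status is already needed for the 110 and 26 targets. Pooling keeps its 86-88% power under a uniform effect. The matched test raises the type I error of the switching rule slightly, to about 5.5-6.0% instead of 5.2-5.7%. An optional fixed sequence, first-line and then the full set, removes the switch and that inflation, but lowers primary power to about 82% if the effect is uniform.

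Two conditions apply. If SAP Part 1 already fixes these points, align the protocol to it. If the data are already unblinded, changing the rule would be post hoc. The SAP Part 2 appendix speaks of randomized-period datasets as already created, so this needs checking. Section 10.3.6 allows the two subgroups to be unblinded at different times, so the rule must be settled before the first of them.
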